Official Title of the Study:

Improving Voluntary Engagement for PTSD Treatment among Service Members

Date:

January 30, 2018

NCT ID:

Not yet assigned

STUDY PROTOCOL

Objectives

This study will develop and test a brief motivational enhancement intervention for active duty Army and Air Force personnel who are experiencing symptoms of PTSD and who are not currently in treatment. The intervention is designed to prompt: (1) a willingness to participate voluntarily in a self-appraisal of PTSD symptoms, (2) increased perceptions of PTSD treatment effectiveness, (3) reduced perceptions of stigma associated with mental healthcare, (4) engagement in PTSD treatment or other self-help programs, and (5) reductions in PTSD symptoms. The proposed study will test the efficacy of this intervention against a comparison condition of treatment-as-usual – written referrals to treatment options.

Hypotheses

H1: Individuals receiving the MET intervention will report more PTSD treatment engagement at follow-up relative to participants in the comparison condition.

H2: Individuals receiving the MET intervention will experience fewer PTSD symptoms at follow-up relative to participants in the comparison condition.

H3: The effect of the intervention on PTSD symptoms will be mediated by PTSD treatment engagement.

H4: The impact of the intervention on PTSD treatment engagement at the 6-month follow-up will be mediated by decreased perceived stigma associated with PTSD treatment and increased perceived effectiveness of treatment for PTSD, both of which will be targeted by the MET intervention.

Methods

Design. In a randomized controlled trial, the experimental (MET) and control (TAU) interventions will be compared. Participants (N = 200) will be randomly assigned to receive the MET condition or TAU. Both interventions will be preceded by telephone-administered screening and baseline assessments. Telephone administered follow-up assessments at 1 week, 3, and 6 months will assess post-intervention change in pertinent intentions, treatment participation, behaviors, symptoms, and perceptions of stigma and treatment effectiveness.

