Hypotheses 1 and 2 evaluate whether MET participants will report more treatment engagement and fewer PTSD symptoms at follow-up than TAU participants. This study will have 4 repeated measures from baseline to 6 months follow-up yielding up to 800 observations. Given the nesting of observations within individuals, we will run linear mixed (also known as hierarchical linear or multilevel) models (Diggle, Heagerty, Liang, & Zeger, 2002) to test study hypotheses. Measures of PTSD symptoms (CAPS) and treatment engagement (TAQ) will be analyzed as outcomes in separate models. Fixed effects will include indicator variables for time (1-week, 3-months, 6-months) with baseline as the reference, intervention condition, and the interaction between time point and condition. The following represents the basic model:

$$\text{Level 1: } Y_{ti} = \pi_0 + \pi_1(\text{Time1wk})_i + \pi_2(\text{Time3m})_i + \pi_3(\text{Time6m})_i$$

$$\text{Level 2: } \pi_0 = \beta_{00} + \beta_{01}(\text{Treat}) + r_{00i}$$

$$\pi_1 = \beta_{10} + \beta_{11}(\text{Treat}) + r_{10i}$$

$$\pi_2 = \beta_{20} + \beta_{21}(\text{Treat}) + r_{20i}$$

$$\pi_3 = \beta_{30} + \beta_{31}(\text{Treat}) + r_{30i}$$

where Y_{ti} represents the continuous outcome for individual i at time t ; Time1wk , Time3m , and Time6m are the indicator variables for study time points where baseline is the reference; Treat represents the variable for intervention condition; and r_{00i} through r_{30i} represent random subject specific deviations from the corresponding overall intercept or slope. Of particular interest are the coefficients β_{11} , β_{21} , and β_{31} , which describe the cross-level interactions between intervention condition and time. For analyses of PTSD symptom score as the outcome, we expect that these interaction terms will be negative and statistically significant suggesting that PTSD symptoms are lower at follow-up visits among those randomized to the MET intervention compared to those in the control group. We will consider inclusion of additional covariates such as gender, social support, and trauma severity to improve precision of estimates. We will also explore modeling time as a continuous measure to assess treatment differences on slopes over time. Similar mixed effects models will be used to test effects of the intervention on stigma/barriers to treatment (PSBCPP) and treatment expectancies (CEQ) as well as secondary outcomes such as anxiety and depression symptoms.

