For analyses involving multiple outcomes, we will guard against Type I error by adjusting criteria for statistical significance for multiple testing (e.g., using global tests that test for an overall difference across outcomes while accounting for their inter-correlation or Benjamini-Hochberg corrections for the false discovery rate) where appropriate.

For hypothesis 3, we will test whether the effect of the intervention on PTSD symptoms will be mediated by PTSD treatment engagement. For hypothesis 4, we will test whether effects of the intervention on treatment engagement are mediated through stigma and treatment expectancies. We will evaluate the effect of the intervention on change in the outcome (e.g., PTSD symptoms) both before and after controlling for the putative mediator(s) (e.g., treatment engagement) using the method described by Krull and MacKinnon (1999; 2001). Reduction in the percentage of variance accounted for by the interaction effect after controlling for the mediator(s) will inform the degree to which the effect is mediated.

Missing Data and Attrition

Based on retention rates in our ongoing clinical trial, we expect no more than 20% attrition by 6-month follow-up in this proposed study. Linear mixed models provide unbiased estimates in the presence of missing data as long as it can be considered ignorable (Atkins, 2005). Missing data are ignorable if they are either missing completely at random or related to variables in the analysis, including earlier time points of the outcome (Graham, 2009). Little efficiency is lost in linear mixed models with 10%-20% missing data. As a safe-guard against the possibility of nonignorable missing data, we will use pattern-mixture models for non-ignorable missing data that directly assess sensitivity of findings to the presence of missing data (Atkins, 2005).

Sample Size and Power

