This study was powered to detect differences in PTSD symptoms between the intervention condition and control group over time. We used a simulation-based approach to estimate power for this study (Gelman & Hill, 2007). Using R statistical software, 1,000 datasets were generated based on the linear mixed model equation provided in the Analysis Plan. Estimates for model parameters for standardized PTSD scores (e.g., baseline intercept, slopes for time, distribution of random effects) were guided by preliminary data from our ongoing clinical trial. We also specified missingness of 13% and 19% at 3- and 6-month follow-up, respectively, according to missing data patterns in the ongoing trial. The model was fit for each of the 1000 datasets. A number of simulation runs were conducted varying the size of the treatment effects and fixing the sample size to 200. The percentage of datasets where the treatment-by-time interactions were statistically significant provides an estimate of power. Based on these simulations, this study should have $>.8$ power to detect effect sizes of $.36$ or greater at any given follow-up visit. An effect size of $.36$ is at the lower end of the range found in the extant literature on treatment for PTSD in military samples. The conservative estimate seems appropriate given the non-treatment seeking nature of the population yet is still clinically meaningful. For instance, a $.35$ effect size translates to a mean difference of approximately 6 points between conditions on the PTSD symptom checklist based on data collected in our current ongoing trial.

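### The H3 and H4 mediation analyses commit to no adjustment for common causes of mediator and outcome, so part of the arm effect can be wrongly credited to the mediator, or real mediation hidden

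*Combined protocol and SAP*

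**What the plan says.** Study Protocol, Hypotheses: H3 makes treatment engagement the mediator of the effect on PTSD symptoms. H4 says that the effect on engagement at 6 months will be "mediated by decreased perceived stigma associated with PTSD treatment and increased perceived effectiveness of treatment for PTSD".

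Statistical Analysis Plan, paragraph on hypotheses 3 and 4: the intervention effect on change in the outcome is evaluated "both before and after controlling for the putative mediator(s) (e.g., treatment engagement"), following a cited multilevel mediation method. The degree of mediation is judged by how much less variance the interaction explains once the mediator is in the model. No confounder, baseline mediator value or assumption about unmeasured confounding is named for these models.

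Statistical Analysis Plan, paragraph on hypotheses 1 and 2: the basic model contains visit indicators, condition and their products. The only covariate statement is "We will consider inclusion of additional covariates such as gender, social support, and trauma severity to improve precision of estimates". Baseline stigma (PSBCPP) and baseline expectancy (CEQ) are not among its examples.

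Missing Data and Attrition: the pattern-mixture models address dropout, not mediator-outcome confounding.

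**The concern.** Random assignment protects the effect of arm on the mediator and of arm on the outcome. It does not protect the path from mediator to outcome, because nobody is randomised to a level of stigma or engagement.

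The plan's own H4 implies the problem. If stigma and perceived effectiveness drive engagement, then engagement, the H3 mediator, has causes that differ between people before randomisation. For H4, someone with low stigma at baseline will tend to have low stigma at follow-up and may engage more, whether or not MET changed that person's stigma. Follow-up stigma entered as observed carries this stable difference, and MET's effect on stigma turns it into apparent mediation. A common cause acting in the opposite direction would mask a real mediated effect.

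H3 and H4 are two of the four hypotheses and carry the trial's account of how MET works.

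**Working it through.** **Inputs from the documents.** "Participants (N = 200) will be randomly assigned to receive the MET condition or TAU" (Design; ratio not stated, 1:1 assumed). "Telephone administered follow-up assessments at 1 week, 3, and 6 months" (Design). "We also specified missingness of 13% and 19% at 3- and 6-month follow-up, respectively" (Sample Size and Power). Effect size .36 (same section).

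**Assumed inputs, not in the documents.** For H4: baseline stigma lowers engagement by g = .3 SD per SD; stigma stability s = .5 to .7; within-person engagement correlation .3 to .7; MET lowers stigma by .4 SD; total effect on engagement .36 SD; true effect of follow-up stigma on engagement zero.

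**1. The plan's own figure.** It claims more than .8 "power to detect effect sizes of $.36$ or greater at any given follow-up visit", for PTSD symptoms; it gives no figure for H3 or H4. A plain two-sample comparison at 100 per arm and two-sided .05 has SE = sqrt(2/100) = .141 and power Phi(.36/.141 - 1.96) = .72. In the plan's mixed model with compound symmetry and within-person correlation .65, the 1-week interaction has SE = sqrt(4 x .35/100) = .118 and power .86. With the stated missingness, 3 and 6 months give .83 and .81. The claim is attainable from a correlation of about .65. It cannot be reproduced exactly, because alpha is not given and the model inputs are said only to be ones that "were guided by preliminary data from our ongoing clinical trial". It does not bear on mediation.

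**2. H4 at one visit, in closed form.** Within arm, with unit variances, follow-up stigma is s x (baseline stigma) plus noise, and engagement is -g x (baseline stigma) plus noise.

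- Spurious path = Cov/Var = -g x s
- Spurious mediated effect = (-.4) x (-g x s)

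| s | path | mediated effect | share of .36 |
|---|---|---|---|
| .5 | -.15 | .060 | 17% |
| .6 | -.18 | .072 | 20% |
| .7 | -.21 | .084 | 23% |

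Given baseline stigma, follow-up stigma and engagement are uncorrelated within arm, so the path is 0. If MET does not move stigma, the product is 0 whatever the confounding.

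**3. H4 with repeated measures (simulated).** The mixed model draws partly on comparisons within a person, where a stable difference cancels, so the bias is generally smaller.

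- Three follow-up visits: the 6-month arm effect falsely shrinks by roughly 4-20% (5-20% with 13%/19% missing; 4-16% in a rerun with complete data). That is .04 x .36 = .014 to .20 x .36 = .072 SD.
- The plan's four waves, complete data: about -2% to 16%, or -.007 to .058 SD. The low end arises when baseline engagement varies but is unrelated to stigma, the high end when stigma shifts engagement equally at every wave.
- Baseline stigma by visit added to the follow-up-visit model: path about 0, with the mediator significant in 5-7% of complete-data runs.

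**4. H3 and masking.** Assume that MET raises the mediator by .5 SD, total effect -.36, no true mediation, and a baseline common cause with effect .4 on the mediator and -.4 on the outcome. In the four-wave model (complete data) the apparent mediated effect is -.044 if the common cause drives change (.044/.36 = 12%) and -.019 if it shifts all waves equally (5%). With the common cause in the model it is about 0.

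For the opposite sign, let the common cause raise both mediator and outcome by .4, with a true path of -.30. At one visit the estimated path is -.30 + .4 x .4 = -.14, so a true mediated effect of .5 x (-.30) = -.15 appears as .5 x (-.14) = -.07. A 6-month simulation adjusted for baseline gave the same value.

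**The case against.** The best case for the plan has four parts.

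- **The plan names no significance rule for mediation.** It looks at a fall in explained variance that will inform the degree of mediation. A reader might infer that a large share of such trials would falsely declare mediation. The documents do not support that: any false-claim rate would need a test that they do not specify and confounder strengths that they do not give. This part stands, so the size is given here as shrinkage of the arm effect. Even that is only the nearest simple analogue of the plan's variance criterion.
- **Baseline is partly handled.** The outcome is analysed as change in a model with a baseline wave, which absorbs some stable differences. This also stands, and it is why the four-wave range reaches zero. It does not adjust for the mediator's baseline, however. For H4 it may remove little: Eligibility Criteria excludes people in current PTSD treatment, so baseline engagement may be close to zero. The documents do not describe TAQ scoring, so this cannot be settled.
- **The cited method may say more.** How the mediator is entered (centred, or split within and between persons) is left to a source outside the documents. It would go too far to say that the analysis will adjust for nothing; the supportable statement is that the plan commits to no adjustment.
- **Covariates are contemplated.** Three are named, but optionally, for precision, and without the baseline mediators.

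**Conclusion.** The point holds as a gap in what the plan commits to. Followed as written, the H3 and H4 models leave the mediator-outcome path open to confounding by baseline differences that the trial appears set to measure. Confidence in the omission is high. The size is conditional: for H4, a false shrinkage of roughly 4-20% on follow-up visits and about -2% to 16% in the four-wave model, under the assumed strengths above and only if MET moves the mediator. At these sizes the likely error is a modest overstatement or understatement of partial mediation, not a wholly invented mechanism. A reader might also infer that the trial's main comparisons are in doubt. They are not: H1, H2 and the stated power rest on randomisation and are unaffected.

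**What to change.** In the Statistical Analysis Plan paragraph on hypotheses 3 and 4, state before outcome data are examined that:

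- **H4 models**, with and without the mediators, include baseline PSBCPP and baseline CEQ with visit interactions.
- **H3 models**, with and without the mediator, include baseline PSBCPP and CEQ (causes of engagement under H4), gender, social support and trauma severity.
- **Where baseline CAPS is a covariate in H3**, the model is fitted to the follow-up visits only. In the four-wave model baseline CAPS is an outcome row, and baseline CAPS by visit would predict that row exactly.
- **Visit interactions** are limited to the baseline mediators and baseline CAPS.
- **A sensitivity analysis** reports the residual mediator-outcome correlation at which the indirect effect would vanish.
- **H3 and H4 conclusions** are worded as conditional on no unmeasured confounding.

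Cost: SAP wording and one added sensitivity analysis. No new data should be needed, since the plan already models PSBCPP and CEQ with baseline as reference and names the other covariates; that they are all collected at baseline should be confirmed. The four-wave H4 model gains 2 x (1 + 3) = 8 parameters. A follow-up-only H3 model gains 3 x (1 + 2) + 3 = 12. Giving six covariates visit interactions in four waves would instead add 6 x (1 + 3) = 24, which is a lot for N = 200. The mechanism claim becomes more guarded, and adjustment cannot remove confounding by variables that are not measured.

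### H3 and H4 (mediation) should be decided by an indirect effect with an interval and a mediator that precedes the outcome; the variance reduction written in the plan cannot do this alone

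*Combined protocol and SAP*

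**What the plan says.** The Hypotheses section gives H3 (engagement mediates the effect on symptoms) and H4 (stigma and perceived effectiveness mediate the effect on engagement at 6 months). Methods, Design places follow-up at 1 week, 3 months and 6 months.

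The Statistical Analysis Plan says of H4 that "we will test whether effects of the intervention on treatment engagement are mediated through stigma and treatment expectancies", and uses the same verb for H3. The intervention effect on change in the outcome is evaluated "both before and after controlling for the putative mediator(s", by a method given by citation. The one summary measure written out is "Reduction in the percentage of variance accounted for by the interaction effect after controlling for the mediator(s", which "will inform the degree to which the effect is mediated".

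The basic model has three treatment-by-time coefficients, "which describe the cross-level interactions between intervention condition and time". The mediators are repeated measures too: "Similar mixed effects models will be used to test effects of the intervention on stigma/barriers to treatment (PSBCPP) and treatment expectancies (CEQ". No visit or time order is given for any mediator. The paragraph on multiple testing concerns multiple outcomes and sets no criterion for mediation.

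**The concern.** A fall in variance explained describes degree; it is not a test. Adding any covariate to a model moves the treatment coefficient, and by chance alone it moves towards zero about half the time. Without an estimate of the indirect effect and its uncertainty, a reader cannot tell a mediated effect from that movement.

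Time order is the second difficulty. If the mediator enters the four-visit model at the same visit as the outcome, symptoms may be driving engagement (H3), or engagement may be changing stigma and expectancy (H4). The before/after comparison cannot tell these apart from the hypothesised direction.

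H3 and H4 are two of the four hypotheses and carry the claim about how the intervention works. Without a written criterion and order, the same data could be reported as mediation or not, after the results are seen.

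**Working it through.** **Plan figures.** The plan gives no power or error figure for H3 or H4. Its one power figure (above .8 at effect size .36, N = 200) is for symptoms. It cannot be reproduced because the variance parameters are not given, and this point does not depend on it.

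**Inputs from the documents.** N = 200, effect size .36, and "missingness of 13% and 19% at 3- and 6-month follow-up, respectively" (Sample Size and Power). With 19% missing, 200 × .81 = 162 completers, or 81 per arm if allocation is equal.

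**Assumed inputs.** All paths (a = treatment to mediator, b = mediator to outcome), the symptom correlation, two-sided 0.05, the 25% mark, and the index. The plan gives no formula for the variance reduction, so I used

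index = 1 − (adjusted effect / unadjusted effect)².

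If half of a -.36 effect is mediated, the adjusted effect is -.18 and the index is 1 − (.18/.36)² = .75.

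**Step 1: why a drop arises by chance.** In a single-level linear model, unadjusted minus adjusted effect equals the estimated a × b. If either true path is zero, the sign of that product is close to a coin flip. Power for a change score with 81 per arm is .63 at a baseline to follow-up correlation of .5 and .84 at .7. If significance and a drop were independent, both would occur in about .63 × .5 = 32% to .84 × .5 = 42% of trials without mediation.

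**Step 2: simulation with a direct effect of -.36 and no mediation.**

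| Rule | Four-visit model, all available data | Single-level check, 162 completers |
|---|---|---|
| Significant effect plus any drop | 33-45% | about 41% |
| Significant effect plus a drop over 25% | 0.6-1.6% | 4.3-5.4% |
| Indirect-effect interval excludes zero | not tabulated for this scenario | about 4-5% |

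The second row depends on which path is absent. With a = 0 and b = -.36, a separate single-level check gave 40% for any drop, 13% for a drop over 25%, and 5% for joint significance of both paths. For the H3 interval with all available data, false positives were 0-6.8% over 20 null scenarios adjusted for baseline and 1-week symptoms.

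**Step 3: time order.** These are median indices from a single-level check with true mediation.

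| How engagement acts | Mediator at 3 months | Mediator at same visit |
|---|---|---|
| With a lag | .74 | .42 |
| Within the last interval | .42 | .73 |

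Neither choice is best in every case. With a same-visit mediator and symptoms driving engagement at .3, the index turned negative (-.13) despite true mediation.

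**Step 4: the H4 rule.** With a = .36 and b = .3 for each mediator, the joint indirect effect was detected in 96% of trials and both separate effects in 52%. At b = .2 the figures were 80% and 14%. False positives for the joint effect were 0.2-3.8%.

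**The case against.** The strongest reply is that the plan names a published method, which may contain a standard error or interval. That stands: the documents do not show what the method supplies. A reader might infer that no test of mediation is planned, and the documents do not support that. They support only that no test is written out. Nor can a citation choose this trial's mediator visits or its rule for two mediators.

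A reader might also infer that H3 lacks an interaction term or an outcome visit. The documents do not support that either. The basic model lists the interaction of time point and condition as one fixed effect, and the mediation paragraph can mean that whole term.

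The variance reduction is worded as a description of degree, so scoring it as a yes/no rule is harsher than the text. This also stands in part: once a significant effect and a drop over 25% are both required, the four-visit rate falls to 0.6-1.6%. But neither requirement is in the plan, and the 13% result shows that such a screen does not protect in every case.

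Finally, H4 is worded to allow both mediators in one model, so the joint-or-separate question is a clarification, not an error.

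**Conclusion.** The point holds as a recommendation. The written variance reduction should not decide H3 or H4, and the time order of mediator and outcome should be stated. The size is the contrast between roughly 33-45% and about 5% when there is a direct effect only. It rests on assumed paths, an assumed index and the any-drop reading, so it shows what the measure can do, not this trial's error rate. That a same-visit mediator leaves reverse causation open follows from the design and needs no simulation. H1 and H2 are untouched.

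**What to change.** 1. **Criterion.** Decide H3 and H4 by an indirect effect (product of coefficients) with a bootstrap or Monte Carlo 95% interval that excludes zero. If the cited method has its own interval, write it out. Keep the variance reduction as descriptive.
2. **Missing data.** Fit to all available data, in line with the plan's own premise: "Linear mixed models provide unbiased estimates in the presence of missing data as long as it can be considered ignorable".
3. **H4.** Take stigma and expectancy at 1 week, adjusted for baseline where measured, with engagement at 6 months as the outcome. State in advance whether the joint or both separate indirect effects decide.
4. **H3.** Use a mediator that precedes the outcome, for example engagement reported at 3 months and CAPS at 6 months, adjusted for baseline and 1-week CAPS. Report engagement at 6 months as a sensitivity analysis, because the best lag depends on when engagement acts and on a TAQ recall window that the documents do not give.

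**Cost.** SAP wording and modest extra analysis; no new visits. Engagement after 3 months is left out of the main H3 estimate. Power depends on the paths: 64-70% at a = .36, b = -.3, and 90-92% at a = .5, b = -.36. If 1-week symptoms drive engagement at .3, adjusting for baseline CAPS alone gave 17-21% false rejections, and adding 1-week CAPS gave 4-6%. Unmeasured mediator-outcome confounding remains: a common cause of .2 or .3 SD gave false positives of 8-11% or 26-31%. The SAP should state this limit.

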Study Population. Study participants will be active duty Army and Air Force personnel stationed at Joint Base Lewis-McCord (JBLM). JBLM has a population of active duty personnel of approximately 46,496 ([name], 2014). The demographic characteristics of the JBLM sample are expected to mirror demographic characteristics of Army and Air Force personnel in general. Participant selection will be equitable – inclusion/exclusion criteria are minimal and there are no limitations on age, race, ethnicity or sex included in the study.

Eligibility Criteria. Eligibility for enrollment and random assignment to the two conditions will be based on the following criteria: 1) current PTSD, 2) not currently being treated (counseling and/or medication) for PTSD, and 3) currently serving in the Army or Air Force. Exclusion criteria include: 1) non-fluency in English, 2) evidence of psychosis, 3) pending deployment that would preclude completion of follow-ups. Callers who do not meet eligibility criteria, but who are concerned about PTSD symptoms, will be provided the opportunity to speak with a counselor and to discuss their thoughts and concerns surrounding their symptoms. Counselors will provide

a 15-45 minute Motivational Interviewing (MI) session focused on their PTSD symptoms, and an exploration of options for ongoing support. Referrals to local treatment agencies and self-help options will also be available to the ineligible caller.

Relevant Scientific Background

Posttraumatic Stress (PTS) is associated with serious health and psychological effects. The health and well-being of military personnel, and consequently the capacity for optimal functioning of military units, are compromised by PTS. Rates of PTS are high among military personnel with post-deployment rates ranging from 5-20% (Hoge et al., 2004). Untreated PTS is associated with high rates of suicide, medical services utilization, relationship impairment, legal difficulties, decreased worker productivity, and decreased military readiness (Hoge et al., 2006; Hoge et al., 2007; Kline et al., 2010; Tanielian et al., 2008).

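### The H1 engagement model leaves out collected predictors of engagement, so its claim to handle dropout without bias is weak where earlier TAQ values say little; the possible bias is modest and of unknown direction

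*Combined protocol and SAP*

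**What the plan says.** - **Condition for unbiasedness** (SAP, Missing Data and Attrition). The mixed models are said to be unbiased if missingness is ignorable: "Missing data are ignorable if they are either missing completely at random or related to variables in the analysis, including earlier time points of the" modelled variable. The same paragraph adds pattern-mixture models as a safeguard against non-ignorable dropout. It does not state patterns, identifying restrictions or outcomes.
- **The H1 model** (SAP, text on Hypotheses 1 and 2). "Measures of PTSD symptoms (CAPS) and treatment engagement (TAQ) will be analyzed as outcomes in separate models". The fixed effects are time, condition and their interaction. Further covariates (the examples are gender, social support and trauma severity) are only to be considered, and for precision. CEQ and PSBCPP are outcomes of their own models.
- **Entry state** (Study Protocol, Eligibility Criteria). Participants must be "not currently being treated (counseling and/or medication) for PTSD".
- **Expected drivers of engagement** (Study Protocol, H4). The effect on engagement "will be mediated by decreased perceived stigma associated with PTSD treatment and increased perceived effectiveness of treatment for PTSD".
- **Expected loss.** Sample Size and Power uses 13% missing at 3 months and 19% at 6 months. Missing Data and Attrition expects at most 20% by 6 months.

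**The concern.** A mixed model recovers a lost participant's later values from what it conditions on. For CAPS, earlier scores should predict later ones, so the SAP's reassurance is reasonable. For TAQ it is weaker. If nearly everyone starts at or near no treatment, and one week leaves little time to begin, a participant lost before 3 months tells the model little beyond arm. The model then in effect gives that person the mean of those who stayed in the same arm.

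The trial does collect measures that its own H4 expects to separate likely engagers from likely non-engagers. Dropout that depends on those measures is not ignorable for a model that omits them, by the SAP's own criterion. It would be ignorable for a model that uses them. What is at stake is the between-arm engagement contrast at 3 and 6 months, which is the test of H1.

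**Working it through.** **The plan's own figure.** The documents give no SD, rate or power for TAQ. The only stated figure concerns PTSD symptoms: "this study should have $>.8$ power to detect effect sizes of $.36$ or greater at any given follow-up visit". It cannot be confirmed or refuted, because alpha, sidedness and the within-person correlation are not given. With two-sided .05 and 81 per arm (100 × .81, assuming 1:1 allocation), a cross-sectional comparison has SE √(2/81) = .157 and power Φ(.36/.157 − 1.96) ≈ .63. Power of .80 needs a baseline-to-6-month correlation of about .67 (change score) or .58 (baseline-adjusted). That is plausible for symptoms, so this point does not challenge the power statement.

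**Step 1: how many have only uninformative values.** Inputs are 13% and 19% missing, from Sample Size and Power. If dropout is monotone (assumed), 13/19 = 68% of those missing at 6 months were already missing at 3 months and have at most baseline and 1-week TAQ. The other 6/19 = 32% also have a 3-month TAQ.

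**Step 2: bias in the 6-month contrast.** This is a large-sample simulation (400,000 per arm) of a mixed-model analysis with 13% and 19% monotone dropout in each arm. The following are assumptions, not document figures:
- early TAQ uninformative
- 3-to-6-month TAQ correlation .6
- correlation of the auxiliary (expectancy or stigma) with TAQ of .2 to .5
- MET shift of .3 SD in the auxiliary
- total effect .36 SD
- dropout odds ratios of .5 to 2 per SD

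| Dropout driven by | Absolute bias, auxiliary omitted (SD) | Absolute bias, auxiliary used (SD) |
|---|---|---|
| Auxiliary, equally in both arms | about 0 | about 0 |
| Auxiliary, differently by arm | about .01 to .10 | at most .005 |
| Engagement itself, differently by arm | .04 to .17 | .04 to .15 |

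Two rows show the sign, both at correlation .5 with the auxiliary omitted. With an odds ratio of .5 in MET only, the bias is +.050. With .5 in TAU only, it is −.056. The largest value, −.098, has odds ratios of .5 in TAU and 2 in MET. As a yardstick only, since .36 is the symptom effect, .013/.36 = 4% and .098/.36 = 27%.

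**Step 3: what 3-month TAQ contributes.** In the largest case the completer bias is −.124 and the mixed-model bias is −.098, a reduction of .026/.124 = 21%. The 3-month value therefore helps, but only partly.

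**Step 4: effect on the error rate.** With bias b and SE .157, the two-sided 5% error becomes P(Z > 1.96 − b/SE) + P(Z < −1.96 − b/SE).
- b = .03: .038 + .016 = 5.4%
- b = .07: b/SE = .445, giving .065 + .008 = 7.3%
- b = .09: b/SE = .573, giving .083 + .006 = 8.8%

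The smaller SE implied by the symptom power statement (.36/2.80 ≈ .129) should not be used here. It needs the baseline correlation of .58 to .67 shown above, which contradicts the premise that baseline TAQ is barely informative.

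**The case against.** **The plan already has a safeguard.** A reader might infer that the SAP simply takes dropout to be ignorable. It does not: pattern-mixture models are promised for the case where that fails, and dropout depending on omitted variables is such a case for this model. This corrects any claim that the risk was overlooked. It does not settle the matter, because the analysis is unspecified and leaves the primary H1 estimate as it is.

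**Differential selection is not shown.** A reader might infer that MET participants who decide against treatment will avoid follow-up calls, so that H1 is inflated in favour of MET. The documents do not support this. The SAP's preceding Summary describes the check-up as a stock-taking exercise free of pressure to change. Stronger selection in TAU reverses the sign, and equal selection gives about no bias. This objection stands as to direction. That selection could differ at all remains plausible, since one arm receives counselling aimed at these beliefs and the other a written referral.

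**Early TAQ may not be uninformative.** TAQ content and scoring are not described, and being untreated at entry need not mean no variation. This is fair: the floor is an inference, and for 1 week a weaker one. The covariate list is also open-ended, though its stated purpose is precision.

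**Auxiliaries do not repair everything.** When dropout depends on engagement itself, most of the bias remains. This stands, and it is the reason to keep and specify the pattern-mixture analysis.

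**The same argument for H2.** A reader might extend the point to CAPS because H3 links engagement to symptoms. Earlier CAPS should be informative and no bias was quantified there, so that extension is not established.

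**Conclusion.** The concern holds in a conditional form. As written, the H1 analysis meets the SAP's ignorability criterion only if dropout does not depend on expectancy or stigma beyond what arm and observed TAQ capture. For roughly two-thirds of those missing at 6 months, observed TAQ probably captures little. If selection on those measures differs by arm, the contrast is off by about .01 to .10 SD in either direction. At SE .157, a bias of .07 to .09 SD takes a nominal 5% test to about 7% to 9%, and a bias of .03 SD to about 5.4%.

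This rests on monotone dropout, 1:1 allocation, weakly informative early TAQ, and assumed correlations and dropout mechanisms, none of which the documents supply. The case for change is that the needed variables are already collected, not that bias has been demonstrated.

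**What to change.** 1. For H1, handle missing follow-up by multiple imputation within arm, using baseline and earlier-visit TAQ, CEQ, PSBCPP and CAPS as auxiliaries. A joint model is an alternative if it suits the TAQ distribution, since the SAP foresees count models for non-normal outcomes.
2. Keep post-randomisation CEQ and PSBCPP out of the H1 outcome model. They are the H4 mediators, and adjusting for them would remove part of the effect.
3. Reword Missing Data and Attrition so that the claim of unbiasedness rests on this enlarged set of variables.
4. Keep the pattern-mixture analysis, state that it applies to TAQ, and give its patterns and identifying restrictions. It addresses dropout that depends on engagement itself.
5. Using the same imputation for H2 is optional.

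**Cost.** SAP wording and one more model to specify, with no new data and no change to the sample size or the stated power. In a check with 100 per arm, regression-based imputation on as many as 8 auxiliaries removed the bias that runs through them with almost no loss of precision.
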